### **3. Methodology**

#### **3.1 Setting and population.**

##### **Research setting.**

This study will take place with Sweetwater Union High School District (SUHSD), a public school district in South San Diego County along the US-Mexico border, that serves 90% racial and ethnic minority students and a high proportion of socioeconomically disadvantaged students (66% of middle school students eligible for free/reduced meals). It is the second largest school district in San Diego County and the largest secondary school district in CA (>39,000 students). It includes middle schools, a junior high, and high schools. The proposed project will focus on ten middle schools and one junior high (10,160 students, 893 staff). The district serves one of the largest proportions of racial and ethnic minority students in the county and CA; 72.4% of students are Latino/a and 8.5% Filipino (vs. 54.9% Latino/a and 3.7% Filipino in San Diego County schools). Over a fifth (21.2%) of students are English-language learners and half speak a language other than English at home. The district's academic year begins on July 21, 2021.

**Study population.** There are 10 middle schools and 1 junior high school eligible for inclusion, all in the Sweetwater Union High School District. Three will be selected to participate in the noninferiority trial. Schools will be excluded from possible selection if they have a lower proportion of students from households receiving Supplemental Nutrition Assistance Program benefits, a lower proportion of underrepresented minority students compared with other schools, have ongoing school-wide testing programs with a commercial provider, cannot be matched to other schools by population size, or are geographically close to another school.

Study participants will be students or staff at the selected SUSHD schools.

**Inclusion criteria:** SUHSD school staff member or student at a school selected for inclusion in the trial. Able to speak English or Spanish.

**Exclusion criteria:** Not a SUHSD student or staff member at a school selected for inclusion in the trial. Not able to speak English or Spanish.

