### **Research design**

#### **Aim 1. At-home rapid antigen COVID-19 testing vs. on-site rapid antigen testing.**

Pragmatic non-inferiority trial, randomizing middle schools to either the on-site or the at-home COVID testing model. Trial duration about 5 months weeks. We will compare participation rates (percentage of the school population participating in testing) and adherence to the testing schedule (percentage of scheduled tests completed).

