#### **Aim 2. Family-based model to increase student and staff participation in testing**

Quasi-experimental trial pre-post control group design. To establish a baseline (pre-test), all three schools will implement the respective testing program without the family-based model for 4 weeks. At the end of the 4 weeks the two schools in Aim 1 will implement the family-based model promoting the availability of testing for unvaccinated family members whereas the control school will not. We will track participation rates (overall and testing schedule adherence) in the three schools for 12-15 weeks post implementation of opening up testing to family members.

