### **3.4 Statistical Analysis Plan**

**Aims 1 and 2.** All analyses will follow the intention-to-treat principle.

This study is designed to determine if at-home COVID-19 testing is noninferior to onsite testing for participation rates and adherence to weekly testing. We selected a noninferiority margin of 6%, because of the significant advantages of an at home COVID-19 testing program in implementation resources and reducing at-school exposures.

The necessary sample size was calculated as 324 per arm (type I error rate 0.05, power 80%) for both outcomes.

We plan to use generalized estimating equations models with a logit link and will evaluate correlation structure selecting correlation structure based on model fit. We anticipate a first-order autoregressive correlation structure to account for the time dependence within each participant. Models including covariates, such as participant type (student, staff), race and ethnicity, primary language spoken at home, gender identity, COVID-19-vaccination status, and prior COVID-19 testing among interaction terms, will be evaluated.

The first outcome, participation rate in testing over time, utilizes the school population sample of both enrolled and non-enrolled participants using school demographic data. Therefore, models for this outcome will only have basic demographic covariates of participant type, race and ethnicity, and gender identity since these demographics were available by school. Estimated marginal means (model predicted probabilities) and standard errors for the outcomes for each study arm, controlling for covariates, will be generated for testing the noninferiority hypotheses. Exploratory subgroup analyses will be conducted for covariates that showed differences between the arms. One-sided noninferiority tests for participation rates and adherence proportions between the 2 study arms will be assessed. One-sided 95% confidence intervals for all models will be constructed.

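### Schools are randomised and at least one arm is a single school, but as written the Aim 1 noninferiority intervals and tests include no between-school variance

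*Combined protocol and SAP*

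**What the plan says.** Section 3.2 (Research design, Aim 1) makes the school the unit of randomisation: "Pragmatic non-inferiority trial, randomizing middle schools to either the on-site or the at-home COVID testing model".

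The number of schools is given in two ways. Section 3.1 (Study population) says "Three will be selected to participate in the noninferiority trial". Section 3.2 (Aim 2) says "the two schools in Aim 1 will implement the family-based model" and sets a further control school beside them. With two arms, that is two schools v one on the first reading and one v one on the second.

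Section 3.4 plans a generalized estimating equations (GEE) model with a logit link. On correlation it says "We anticipate a first-order autoregressive correlation structure to account for the time dependence within each participant", and that the team "will evaluate correlation structure selecting correlation structure based on model fit". The covariates listed are personal characteristics, and the participation model is limited to participant type, race and ethnicity, and gender identity. Noninferiority is tested on covariate-adjusted marginal means. On the margin it says "We selected a noninferiority margin of 6" percent, without giving the scale. On precision it says "The necessary sample size was calculated as 324 per arm (type I error rate 0.05, power 80%) for both outcomes" and "One-sided 95% confidence intervals for all models will be constructed".

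**The concern.** People in one school share staff, outreach, local attitudes and local case rates, so their testing behaviour can be correlated. A GEE whose clusters are participants treats people in the same school as independent, whichever working structure fits best. Choosing among within-participant structures does not add a school level.

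The intervals and tests decide Aim 1 for both primary outcomes. If the schools would have differed under the same testing model, that difference is added to the arm contrast, and the standard error makes no allowance for it. The error that matters is a false finding of noninferiority, which would support replacing on-site testing with home kits. Section 3.4 neither states the assumption of no school difference nor shows how large a difference would overturn the conclusion.

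**Working it through.** **Inputs from the documents.** Margin 6% (taken here as percentage points), type I error 0.05, power 80%, 324 per arm, one-sided 95% intervals (section 3.4). Three schools (section 3.1) or two (section 3.2, Aim 2). 10,160 students and 893 staff in 11 schools (section 3.1), so 11,053/11 ≈ 1,005 people per school on average.

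**Assumptions.** The documents give no ICC, so a range is used. The selected schools are taken to be of average size. There is one observation per person, and a normal approximation is used.

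**1. The plan's own figure.** No expected rate is given, so 324 cannot be reproduced from stated inputs. Solving backwards with no allowance for clustering, n = 2p(1−p)(1.645 + 0.842)²/0.06² gives 324 at a common rate of about 10.5% or 89.5%. That solution is not unique. One-sided 0.025 gives 324 at about 8.1% or 91.9%. At 95%, n is 163, and a design effect of 1.99 also gives 324.

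**2. Error of the planned test at the margin.** With k schools and n people per arm:

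- Var_naive = p₁(1−p₁)/n₁ + p₂(1−p₂)/n₂
- Var_true = ICC × [p₁(1−p₁)/k₁ + p₂(1−p₂)/k₂] + (1−ICC) × Var_naive
- Error = 1 − Φ(1.645 × √(Var_naive/Var_true))

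Example: 324 per arm, one school each, ICC 0.01. The variance ratio is 0.99 + 0.01 × 324 = 4.23; 1.645/√4.23 = 0.80; the error is 21.2%.

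| Residual ICC | 324 per arm, 1 v 1 | 324 per arm, 2 v 1 | 1,005 per school (participation) |
|---|---|---|---|
| 0.0001 | 5.3% | 5.2% | 5.8% |
| 0.001 | 7.6% | 7.0% | 12.3% |
| 0.005 | 15.5% | 13.4% | 25.1% |
| 0.01 | 21.2% | 18.7% | 31.0% |

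The first and last columns do not depend on the outcome rate, and the last is the same at 1 v 1 and 2 v 1. The middle column assumes the same p(1−p) in both arms. With 4.5% at home v 10.5% on site and ICC 0.01, it is 19.7% if the home arm has two schools and 17.6% if the on-site arm does.

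Repeated weekly tests shrink the naive variance but not the school component. With a 16-week mean (4 + 12 weeks) and an assumed AR(1) of 0.95 to 0.8, the 1 v 1 error with 324 per arm is 8.4 to 10.9% at ICC 0.001.

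**3. Limit that needs no rate, sample size or ICC.** With equal estimated rates, noninferiority requires 1.645 × SE < 6 points. As the sampling error goes to zero, SE tends to SD × √(1/k₁ + 1/k₂), where SD is the residual between-school SD. The largest tolerable SD is then:

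- 1 v 1: 6/(1.645 × √2) = 2.58 points
- 2 v 1: 6/(1.645 × √1.5) = 2.98 points

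**4. Power.** If 324 assumed about 10.5% or 89.5% and no clustering, the naive SE is 0.0241. At 1 v 1, the SE with school variance is 0.0278 at ICC 0.001 and 0.0496 at ICC 0.01. Power, Φ(0.06/SE − 1.645), falls from 80% to about 70% and 33%.

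**5. Can the model supply the missing variance?** No. At 1 v 1, arm and school are the same variable, so between-school variance is not estimable. At 2 v 1 it has one degree of freedom, where the one-sided 95% t value is 6.31 instead of 1.645.

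**The case against.** The case for the plan has several parts.

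- **The cluster variable is not declared.** This is correct. That participants are the clusters is inferred from the AR(1) sentence, since correlation over weeks makes sense within a person. The inference is reasonable, and no other unit is named.
- **The contrast is adjusted.** This is also correct. A reader might infer that the plan compares raw observed rates between schools. It does not: the tests use covariate-adjusted marginal means, so what matters is the school difference left after adjustment. For adherence the candidate covariates include vaccination status and prior testing; for participation they are basic demographics only.
- **Schools are chosen to be alike, and mitigation measures will be accounted for** (section 3.1; section 3.3, Monitoring of safety and mitigation measures). Both may reduce the residual difference. Neither puts what remains into the standard error.
- **Much of the size is assumed.** This stands. No ICC, expected rate, weekly correlation or margin scale is given, and at ICC 0.0001 the inflation is trivial.
- **It is a design limitation that no analysis removes.** This is largely true, and it is why the remedy is disclosure and a sensitivity analysis instead of another model. A reader might infer that clustering the standard errors on school would suffice; with two or three schools it would not.

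The four-week baseline in Aim 2 does not help either, because each school already runs its assigned testing programme during it.

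**Conclusion.** The concern holds. As written, the intervals and tests that decide Aim 1 include no between-school variance, although schools are randomised and at least one arm is a single school. They are too narrow for a claim about the testing model unless the residual school difference is negligible. The inflation runs from almost nothing at ICC 0.0001 to 21% (324 per arm, 1 v 1) or 31% (participation, 1,005 per school) at ICC 0.01. The limits of 2.6 and 3.0 points rest only on a percentage-point margin and equal estimated rates.

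Two stronger readings are not supported. A reader might infer that the true error is some particular figure, or that a noninferiority finding would be false; without an ICC, neither follows. A reader might also infer that 324 ignored clustering. It is consistent with no design effect at about 10.5% or 89.5%, but the derivation is not given and other combinations reach the same number.

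**What to change.** In section 3.4:

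1. State that the school is the unit of randomisation. Reconcile sections 3.1 and 3.2 (Aim 2) on how many schools enter Aim 1 and how many are in each arm.
2. State that the GEE interval describes the covariate-adjusted difference between the participating schools. State also that attributing it to the testing model, even in those schools, assumes no residual school difference after adjustment. Word the Aim 1 conclusion to match.
3. Prespecify, for each outcome, a sensitivity analysis with SE_total² = SE_GEE² + ICC × [p_home(1−p_home)/k_home + p_onsite(1−p_onsite)/k_onsite]. Here p is each arm's estimated marginal mean, k the schools per arm and ICC the residual between-school ICC. Keep the terms arm-specific: a pooled p is miscalibrated at 2 v 1. Next to any noninferiority statement, report the tipping ICC at which it is lost and the matching between-school SD in percentage points. Any grid of ICC values is illustrative, and should include 0 and values below 0.001.
4. Give the derivation of 324 per arm: expected rate, margin scale and any design effect. If there is no clustering allowance, say that the 80% power assumes zero between-school variance.

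The cost is SAP wording and a short calculation on existing output; the planned GEE stays and no schools or participants are added. The price is a narrower claim and wider sensitivity intervals. A claim about the testing model in general would need more schools per arm, which this change does not require.

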### **Study variables**

#### **Primary outcomes:**

- Aim 1. At-home testing vs. on-site rapid antigen testing (testing rate)
  - Participation rate: weekly percentage of students and staff (school population) who participate in testing
  - Adherence to testing schedule: percentage of scheduled weekly tests completed once a participant enrolls in the trial
- Aim 2. Family -based model to increase student and staff participation in testing
  - Participation rate over time: percentage of students and staff who participate in testing
  - Adherence to testing schedule: percentage of scheduled tests completed

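### Does testing participation on estimated marginal means, with no averaging weights stated, mean the test could miss the defined outcome?

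*Combined protocol and SAP*

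**What the plan says.** The Aim 1 research design compares "participation rates (percentage of the school population participating in testing"), and the primary outcomes list repeats the definition: "Participation rate: weekly percentage of students and staff (school population) who participate in testing". Each student or staff member therefore counts once.

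Section 3.4 fits a logit GEE. For participation, the analysis "utilizes the school population sample of both enrolled and non-enrolled participants using school demographic data", and the "models for this outcome will only have basic demographic covariates of participant type, race and ethnicity, and gender identity". For models with covariates more generally, the text ends "prior COVID-19 testing among interaction terms, will be evaluated", so interactions are possible but not named. The quantity on which noninferiority is tested is then given as: "Estimated marginal means (model predicted probabilities) and standard errors for the outcomes for each study arm, controlling for covariates, will be generated for testing". The section states no averaging weights, no averaging scale and no rule for combining weeks.

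On the mix, the research setting describes "ten middle schools and one junior high (10,160 students, 893 staff") and reports that "72.4% of students are Latino/a and 8.5% Filipino". The mix in the three trial schools is not given.

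**The concern.** Estimated marginal means can be averaged in more than one way. One is to average predictions over the people in the data. Another is to give every level of each factor the same weight. When the levels are very unequal in size, the two can differ. Here staff are a small minority of the school population, and the ethnic groups are also far from equal in size.

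Under equal weights, staff behaviour would drive half of the tested difference, which would no longer be the percentage of the school population that the plan defines. At stake is the primary noninferiority conclusion: a shortfall beyond the margin could look acceptable, or an acceptable one could look too large.

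**Working it through.** **Inputs from the document.** Students 10,160 and staff 893 (section 3.1, 11 eligible schools); margin 6% (section 3.4), read here as percentage points, which is an assumption because the scale is not stated. The plan gives no figure for the weighting, so there is nothing of its own to reproduce. All participation rates below are assumed.

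**Staff share.** w = 893 / (10,160 + 893) = 893 / 11,053 = 0.0808, or 8.1%. Equal weighting raises this to 50%, about 6.2 times as much (0.5 / 0.0808).

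**Two ways of averaging, for each arm.**
- Population-weighted: (1 - w) × student rate + w × staff rate.
- Equal-weight: expit of [logit(student rate) + logit(staff rate)] / 2.

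The difference is at-home minus on-site, in percentage points.

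| Assumed rates, on-site to at-home | Population-weighted | Equal-weight |
|---|---|---|
| Students 20% to 15%, staff 40% to 32% | 21.62 to 16.37: -5.24 | 28.99 to 22.37: -6.62 |
| Students 30% to 23%, staff 10% to 7.2% | 28.38 to 21.72: -6.66 | 17.91 to 13.21: -4.70 |
| Students and staff both 20% to 14% | -6.00 | -6.00 |
| Students 50% to 42%, staff 50% to 50% | -7.35 | -4.03 |

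The weights matter, not the scale: equal weights on the probability scale give -6.50 and -4.90 in the first two rows, and population weights on the logit scale give -5.26 and -6.63.

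**Size of the shift under a common odds ratio.** Fix the population-weighted difference at -6.00, solve for the odds ratio, and read off the equal-weight difference:

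| On-site students | Staff 10 points lower | Staff 10 points higher | Staff 20 points higher |
|---|---|---|---|
| 20% | -4.66 | -6.89 | -7.60 |
| 30% | -5.34 | -6.48 | -6.87 |
| 40% | -5.67 | -6.23 | -6.38 |
| 50% | -5.90 | -6.02 | -5.94 |
| 60% | -6.10 | -5.80 | -5.43 |
| 70% | -6.34 | -5.49 | -4.56 |

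The largest shift is 1.6 points (7.60 - 6.00). For students at 40% to 60% it is at most 0.57. That reassurance holds only without an arm-by-type interaction: in the last row of the first table the on-site rates are equal at 50%, and the two averages still differ by 3.3 points (7.35 - 4.03 = 3.32).

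**Which reading the text supports.** Set three statements side by side. The outcome is a percentage of the school population. The participation model is fitted to the school population, enrolled or not. The marginal means are glossed as model-predicted probabilities. Averaging those predictions over the people in the model gives the defined outcome, standardised for covariates. Equal weighting fits the gloss less well and contradicts the outcome definition; the document mentions neither it nor any software default.

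**The case for a change.** The strongest case for a change is this. Naming the school population as the analysis data settles which records enter the model, not how marginal means are formed afterwards. The means are the quantity on which a primary hypothesis is tested, equal weighting is in common use, and one sentence would stop the weights being chosen after the results are seen. Nor does the plan's sample size point to rates near 50%: with equal true rates and one-sided 0.05, 324 per arm follows only at about 10.5% or 89.5%, whereas 50% would need 859.

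Part of this stands. The averaging is unstated, and so are the combination of weeks and the scale of the margin. The arithmetic is correct, and the shift can go in either direction.

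It does not establish a fault. For the conclusion to change, the analyst would have to use equal weights against the outcome definition, participant type would have to stay in the model, an arm difference would have to exist, staff and students would have to differ in rate or in arm effect, and the true difference would have to lie near the margin. The document gives no participation rates, so the last three cannot be checked. The rows that straddle 6 points show that a crossing is possible, not that it is likely. The 324 does not help, because no expected rate is stated and the figure is given for both outcomes. No departure has been calculated for race and ethnicity, for which the document gives district student percentages only. Error rates cannot usefully be attached either: schools are randomised and testing is weekly, and the document gives neither the between-school variation nor the correlation between weeks.

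**Conclusion.** The gap is one of wording, and analysts can fill it sensibly. Averaging model predictions over the school population sample agrees with the outcome as defined twice in the protocol and with the data set named in section 3.4. Under that reading the test addresses the defined outcome, and a sentence on weights would only record what the definition already implies.

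Equal weighting would raise the staff share from about 8.1% to 50%. Under a common odds ratio and the assumed rates in the grid, it would move a -6.0 point difference by up to 1.6 points; with an interaction the shift could be larger (3.3 points in the example). It would be zero if staff and students had the same rates and the same arm effect. These sizes rest on assumed participation rates, on the staff share of the 11 eligible schools applying to the trial schools, and on reading the margin as percentage points. They describe a reading that the document neither states nor favours, so no change to the plan follows.

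### Exploratory subgroups are picked by whether a covariate differs between arms, which tracks school composition rather than whether the testing-model effect varies

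*Combined protocol and SAP*

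**What the plan says.** The subgroup rule is one sentence in Section 3.4: "Exploratory subgroup analyses will be conducted for covariates that showed differences between the arms". The section gives no list of subgroups, no threshold or test for deciding that a covariate differs, and no effect-modification criterion.

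Three other statements bear on it:

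- **Design.** Section 3.2, Aim 1, describes a "Pragmatic non-inferiority trial, randomizing middle schools to either the on-site or the at-home COVID testing model". Section 3.1 says "Three will be selected to participate in the noninferiority trial", while Section 3.2, Aim 2, says "the two schools in Aim 1 will implement the family-based model". The Aim 1 contrast therefore appears to have one school per arm, and at most three schools in all.
- **Covariates.** Section 3.4 gives six examples: participant type, race and ethnicity, home language, gender identity, vaccination status and prior testing. It ends that list with "prior COVID-19 testing among interaction terms, will be evaluated". For participation, "models for this outcome will only have basic demographic covariates of participant type, race and ethnicity, and gender identity".
- **Adjustment.** The arm-specific marginal means used for the non-inferiority tests are to be adjusted for covariates.

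**The concern.** Two questions are being mixed. Whether a covariate is distributed differently in the two arms is a question of balance, and the answer to imbalance is adjustment. Whether the difference between at-home and on-site testing changes across levels of a covariate is a question of effect modification. That is answered by an arm-by-covariate interaction, whether or not the arms are balanced. The plan uses the first question to decide where to look for the second.

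The design sharpens the problem. With whole schools allocated and apparently one per arm, a covariate difference between arms is a difference between two schools. A different pair of schools would give a different set of subgroup analyses under the same plan. A covariate with similar distributions in the two schools would not be reliably selected, even if the effect differed across its levels. Participant type could be such a covariate if staff-to-student ratios are alike.

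At stake is the usefulness of the exploratory subgroup results. The non-inferiority tests for participation and adherence do not depend on this rule.

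**Working it through.** **The plan's own figure.** The only calculated number in Section 3.4 is the sample size: "The necessary sample size was calculated as 324 per arm (type I error rate 0.05, power 80%) for both outcomes". It cannot be reproduced, because no expected rate is stated. With equal true rates and the 6% margin read as percentage points, n = 2p(1−p)(1.645 + 0.842)²/0.06². Setting n = 324 gives p(1−p) = 0.0943, so p is about 10.5% or 89.5% at one-sided 0.05. The present point does not depend on it; 324 is used below only as a convenient arm size.

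**Inputs from the documents.** Section 3.1 gives 10,160 students, 893 staff and 11 schools. The averages are 10,160/11 = 924 students, 893/11 = 81 staff, and 11,053/11 = 1,005 people per school.

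**Assumptions, not in the documents.** A covariate is taken to differ when a two-sided 5% test says so. Individuals are treated as independent. Covariate prevalence and outcome rate are 50% unless stated.

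**1. How easily the trigger fires.** With 1,005 per arm, the standard error of a difference in a covariate near 50% is √(2 × 0.25/1005) = 0.0223. A 5-point gap in school composition gives z = 0.05/0.0223 = 2.24, enough to trigger a subgroup analysis with no effect difference at all. The result varies with gap and arm size. For a covariate at 72% in one arm, the chance of being flagged is:

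| Gap in composition | 324 per arm | 924 per arm |
|---|---|---|
| 5 points | 28% | 65% |
| 8 points | 59% | 96% |
| 10 points | 77% | 99.6% |

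**2. Does the trigger find effect modification?** A simulation of 4,000 runs with a binary covariate compared selection by imbalance with selection by an interaction test:

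| Scenario | n per arm | Imbalance rule selects | Interaction test selects |
|---|---|---|---|
| Balanced; effect differs by 20 points between levels | 324 | 5% | 73% |
| Balanced; effect differs by 20 points between levels | 924 | 5% | 99% |
| Imbalanced by 12 points; no effect difference | 324 | 88% | 5% |
| Imbalanced by 12 points; no effect difference | 924 | nearly 100% | 5% |

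Hand checks at 324 per arm agree. The interaction has standard error √((3 × 0.25 + 0.21)/162) = 0.077, so z = 0.20/0.077 = 2.6. The 12-point imbalance has standard error √(2 × 0.56 × 0.44/324) = 0.039, so z = 0.12/0.039 = 3.1.

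**3. Chance flags.** If covariates were screened independently at 5% with no true difference, the probability of at least one flag is 1 − 0.95⁶ = 26.5% for six covariates. For the three available for participation it is 1 − 0.95³ = 14.3%.

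**4. Precision of the alternative.** For staff, with 81 per arm, the standard error of the arm difference is √(2 × 0.25/81) = 7.9 points at a 50% rate. At a 10% rate it is √(2 × 0.09/81) = 4.7 points. At 50% the staff-versus-student interaction has standard error √(2 × 0.25/81 + 2 × 0.25/924) = 8.2 points, a 95% half-width of 1.96 × 8.2 = 16 points. Adherence covers enrolled participants only, so its cells will be smaller than these rosters.

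**The case against.** Four arguments can be made for the plan.

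- **The sentence may mean something else.** It follows directly on the description of adjusted marginal means by arm. It could loosely refer to covariates for which modelled outcomes differed by arm, which is close to effect modification. The text does not say this. Even on that reading, selection is data-driven with no stated criterion, and the same fixed list resolves it. That the sentence can be read two ways is itself a reason to rewrite it.
- **Interactions are planned.** Section 3.4 does say that interaction terms will be evaluated, and participant type heads its list of covariates. A reader might infer from the subgroup rule that balanced covariates would never be examined. The documents do not support that: one could be flagged by chance or enter an interaction model. What stands is that the interactions are not specified as being with arm and have no stated link to subgroup choice.
- **Imbalance is already dealt with.** This stands. Covariate adjustment is in the plan and nothing needs adding to it.
- **The illustration rests on an assumed trigger.** This also stands. The plan states no test, and the standard errors ignore the allocation of whole schools. The figures show that the two criteria measure different things; they do not predict what the trial would find.

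**Conclusion.** The point holds as a minor defect in an exploratory analysis. On its plain reading, the rule selects on school composition. Under the stated assumptions it picks a balanced effect modifier no more often than chance (about 5%) and usually picks an imbalanced covariate that modifies nothing (about 88% at 324 per arm). This rests on the literal reading of one sentence and on the apparent allocation of one school per arm.

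Two larger claims do not follow. A reader might suppose that the subgroup results are meant to decide who moves to at-home testing. No section says so: the analyses are labelled exploratory, and scale-up belongs to Aim 3, which Section 2 places outside the trial. A reader might also suppose that the non-inferiority conclusion is weakened. It is not, because those tests use the adjusted arm estimates and do not draw on the subgroup analyses.

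**What to change.** Replace the sentence in Section 3.4 with a fixed list of covariates the section already names:

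- **Participation:** participant type, race and ethnicity, gender identity.
- **Adherence:** those three, plus home language, vaccination status and prior testing.

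For each covariate, whatever its balance, report the at-home minus on-site difference within each level and the arm-by-covariate interaction estimate with its confidence interval. State that these are the interaction terms the section refers to. Leave imbalance to the covariate adjustment already planned. Label all of these results exploratory, and state that with so few schools subgroup effects remain confounded with school.

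The change is a short text edit and needs no new data. It has a modest cost: three covariates for one outcome and six for the other make nine covariate-by-outcome analyses. Intervals will be wide in small groups; for staff, the standard error of about 7.9 points at a 50% rate exceeds the 6% margin. The list would no longer depend on which schools were drawn, although the estimates still would.
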